Exhibit A: Study Services and Compensation

Title	Complications and 1-Year Outcomes following hiatal hernia repair with MIROMESH a novel, highly vascular, porcine derived, biologic matrix
Miromatrix Product	MIROMESH® Biologic Matrix
Sponsor	Miromatrix Medical Inc [name]
Protocol Number	2017001 Version 2
Sponsor Contact	M. [name]. [contact] [name] [contact]
Principal Investigator	G. [name]
Study Center	Virginia Heartburn and Hernia Institute [name]
Planned Sample Size	70 consecutive subjects at least 1-year post-index procedure
Study Population	Consecutive cohort of patients who have undergone a hiatal hernia repair between 1 Jul 2015 and 1 June 2016 
 • A minimum of three attempts to reach each subject in the cohort shall be made
Study Objectives	
Primary Objective Characterize the procedural and early post-operative safety profile of MIROMESH when used as reinforcement in hiatal hernia repair.
 
Secondary Objectives Identify a consecutive cohort who may be tracked long term to identify survival of repair. Identify a consecutive cohort who may be tracked long term to characterize mid- and long-term clinical outcomes. Identify a consecutive cohort who may be tracked long term to further characterize the safety profile over time.

Study Design	This will be a retrospective chart review to identify the appropriate cohort with a prospective follow-up survey to acquire safety and outcome information.
Study Assessments and Time Points	
Preoperative – Chart Review A retrospective chart review of appropriate subjects.
 
Data to be acquired will be:
 
 • Gender • Date of birth • Weight • BMI

	
 • Specific diagnosis • DeMeester Score • 24 hour pH test (% acid exposure in 24 hours) • GERD-HRQL Score 
Peri-operative Preoperative – Chart Review
 
 • Date of surgery • Number of stitches used to close wound • Paraesophageal hernia type • Mesh shape • Mesh size used • Attachment technique • Length of stay • Complications 
Post-Operative (With-in 1 month of surgery) Preoperative – Chart Review
 
 • Complications (Mesh related) • Complications (procedure related) • Prolonged dysphagia (Y/N) • Stenosis (Y/N) • Dilations (Y/N) • EGD/UGL documented hernia recurrence • GERD-HRQL Score 
Minimum 1-year Follow-Up Telephone Interview
 
 • Have you had a revision surgery? • GERD-HRQL Score • How satisfied are you with the procedure? • How likely are you to recommend this procedure to a loved one?
Timeline	Data collection will be complete 3-months after approval and funding
Assessment Tools	Patient Charts DeMeester Score 24 hour pH test (% acid exposure in 24 hours) GERD-HRQL Score
Project Budget	\$15,000 and IRB fees as invoiced (or directly paid) 
 • 25% upon full execution of agreement • 25% Upon receipt of spreadsheet showing 50% (35 subjects) completion • 25% upon receipt of spreadsheet with all subject data (70 subjects) • 25% upon receipt of study report – narrative style
Privacy Considerations	Principle Investigator and Sponsor will enter into a Limited-Data Set Data Use Agreement consistent with 45 CFR 164.514. Data listed above will be transferred and no protected health information not specifically covered by the data use agreement will be delivered to the sponsor.
Informed Consent	All subjects will be required to give verbal consent, via the telephone interview, for participation in this study. Subjects will be informed that they were chosen

	
based on the procedure and mesh they received. They will be informed that historical data regarding their pathology and procedure will be gathered and that they will be asked several questions about their current health. They will be informed that, except for, information used to determine age and date of surgery, no protected health information will be used. Subjects that elect to participate will be informed that they will receive a copy of the verbal informed consent.
 
Investigator will mail a copy of the consent script to all subjects who elect to participate in this study.

Ethical Considerations	This Study Proposal Summary will be reviewed by an accredited institutional review board and will not be initiated until written approval has been received.
Statistical Analysis	Descriptive statistics including but not limited to mean, standard deviation, frequency and percentages will be used to describe demographics, medical history, and characterize baseline variable as appropriate. Inferential statistics will be used to describe changes in variable over time.
Deliverable(s)	Excel spreadsheet with all data as outlined above Narrative study report outlining results and drawing conclusions.

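### First-month safety comes from chart review with no field for whether the patient was seen, so 'seen and well' cannot be reliably told apart from 'not seen', and some care given elsewhere is missed

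*Combined protocol and SAP*

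**What the plan says.** The Primary Objective reads "Characterize the procedural and early post-operative safety profile of MIROMESH when used as reinforcement in hiatal hernia repair". The planned sample is "70 consecutive subjects at least 1-year post-index procedure", at one named centre.

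Under Study Assessments and Time Points, the first-month block is headed "Post-Operative (With-in 1 month of surgery) Preoperative – Chart Review". The stray word 'Preoperative' aside, I read this as chart review of the first month. The block has seven items:

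- two complication items (mesh-related and procedure-related), with no stated format;
- three items marked Y/N: dysphagia, listed as "Prolonged dysphagia (Y/N", stenosis and dilations;
- hernia recurrence documented by endoscopy or upper GI study, with no stated format;
- a GERD-HRQL score.

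The source row reads "Assessment Tools Patient Charts"; it does not say whose charts. The surgery date is the only date listed for the operation or anything after it. There is no post-operative contact field and no code for an item that was not documented.

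The interview at one year or more has four questions. One concerns safety: "Have you had a revision surgery". The Statistical Analysis row promises descriptive statistics for demographics, history and baseline variables, and inferential statistics for change over time. It gives no denominator or missing-data rule for complications.

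**The concern.** A retrospective chart can show that a complication was recorded. It shows that none occurred only if someone saw the patient and the relevant care reached the chart. The listed fields capture neither condition. Two kinds of patient may therefore look the same as a patient who was seen and well:

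1. A patient with no documented clinical contact in the first month.
2. A patient treated at another hospital or clinic, without reoperation, whose records never reached the chart.

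The second always lowers the reported rate. The first does so if an empty entry is read as 'no', and the plan does not say how an empty entry is to be read. At stake are the early complication rates that the study exists to report. A reader of the spreadsheet and narrative report could not tell how many of the 70 patients those rates rest on.

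**Working it through.** **The plan's own figures.** No event rate, precision target or power lies behind N = 70, so it cannot be reproduced. The one checkable figure, 35 subjects as 50% completion, is right: 0.5 × 70 = 35. The documents give no share of patients without first-month contact, no share treated elsewhere and no complication rate. Everything below rests on assumed values and shows only how the problem scales.

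**1. No documented contact.** Let m be the share without documented contact (assumed) and x the recorded events (6, assumed).

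- Undocumented patients: u = 70m
- Rate over all patients, which is also the lower bound (all undocumented are 'no'): x/70
- Rate over patients with documented contact: x/(70 − u)
- Upper bound (all undocumented are 'yes'): (x + u)/70

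Intervals are exact (Clopper-Pearson) 95%.

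| m | u | Over all 70 | Over documented | Upper bound |
|---|---|---|---|---|
| 10% | 7 | 6/70 = 8.6% (3.2–17.7) | 6/63 = 9.5% (3.6–19.6) | 13/70 = 18.6% |
| 20% | 14 | 6/70 = 8.6% (3.2–17.7) | 6/56 = 10.7% (4.0–21.9) | 20/70 = 28.6% |

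Changing the denominator moves the rate by 0.9 to 2.1 percentage points, well inside the sampling interval. The bounds are far wider: 8.6% to 28.6% at m = 20%.

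If blanks are read as 'no' and unseen patients carry the same risk, the expected recorded rate is the true rate × (1 − m). A true 10% is then recorded as 9% at m = 10% and 8% at m = 20%.

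With no recorded events, the upper 95% limit is 1 − 0.025^(1/n). This gives 5.1% for n = 70, 5.7% for n = 63 and 6.4% for n = 56.

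**2. Treatment elsewhere.** Suppose 7 patients truly have an early event: 7/70 = 10.0% (4.1–19.5). Let k of them be treated elsewhere without reoperation and never reach the chart. The reported rate is (7 − k)/70:

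- k = 1: 6/70 = 8.6%
- k = 2: 5/70 = 7.1% (2.4–15.9)
- k = 3: 4/70 = 5.7%

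This loss occurs however blanks are coded, and no listed field would recover it.

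**3. Can another listed item fill the gap?** A recorded one-month GERD-HRQL score shows that the patient was assessed in the window. A missing score does not show the reverse, since a patient may be seen without completing the questionnaire. The revision question has no limit on site or time, so it can catch an early reoperation elsewhere. It cannot catch a dilation, an admission or treated dysphagia. Both items help, but neither closes the gap.

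**The case against.** The strongest reply is that the plan never says an unseen patient is event-free. A Y/N label describes the type of answer; it does not forbid a blank or tell the abstractor to read silence as 'no'. The document is a short study summary attached to a contract, so its silence on coding is weak evidence of a wrong rule. **This stands.** A reader might infer that every unseen patient is counted as event-free, or that only the centre's own records are used. The text supports neither. It is silent on blanks, names patient charts without limiting whose they are, and marks only three of the seven items Y/N. Outside records filed in the chart would count.

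Two narrower replies also stand. The procedural half of the objective (peri-operative complications, length of stay) comes from the operative admission and is largely unaffected. And the study is descriptive, with no hypothesis or threshold that a shift of one or two points could overturn.

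It can also be said that limiting the analysis to patients with documented contact brings its own bias: if well patients are less likely to return, the rate is overstated. That is a fair reason not to make this group the sole or main denominator. It is a reason to show both denominators and both bounds.

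None of this supplies the missing information. If blanks are left blank, the plan still has no rule for the denominator, and early care elsewhere without reoperation still goes unrecorded.

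**Conclusion.** The point holds as a cheap improvement to what is collected. For the early post-operative half of the primary objective, the listed fields do not reliably separate 'seen and well' from 'not seen'. They also miss non-reoperative early complications treated elsewhere that never reached the chart. The second gap biases the rates downward; the first does so only if undocumented items are entered as 'no', which the plan leaves open.

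The size cannot be derived from the documents. Under an assumed 10–20% without documented contact, 6 recorded events give 8.6% over all 70 and 9.5–10.7% over those with contact. The upper bound is 18.6–28.6%. The modest change of denominator matters less than the width of those bounds, which the planned spreadsheet would not let anyone calculate with confidence. The further claim that the planned data offer no way at all to detect the problem is not supported, because the one-month GERD-HRQL score is a partial marker of contact.

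**What to change.** 1. **Contact and coding.** Add one field, *clinical contact documented within 1 month: yes/no*, or days from surgery to last contact in that month. Either avoids a new calendar date. Code each first-month safety item, including the two complication items, as *Yes / No, documented / Not documented*.
2. **Reporting.** Give each early rate over all patients and over patients with documented contact. Add a lower bound (undocumented all 'no') and an upper bound (undocumented all 'yes').
3. **One question on the planned call.** *In the first month after this operation, were you admitted or treated for a problem at any other hospital or clinic?* Report chart-only and chart-plus-call rates side by side. Consent is taken on this call, so every participant is reached anyway.

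The cost is one field, one code and one question. Recall after a year or more is imperfect, which is why the two rates should be kept apart, and the results may look slightly less favourable. The consent script, which describes the questions as being about present health, and the list of data to be transferred under the data use agreement need a small update to cover the additions.

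### After the first post-operative month, revision is recorded only by an undated yes/no question at a call made at 12 months or later, so a 'yes' cannot be placed before or after 12 months

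*Combined protocol and SAP*

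**What the plan says.** All references are to the combined protocol and SAP.

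- **Title:** "Complications and 1-Year Outcomes following hiatal hernia repair with MIROMESH".
- **Planned Sample Size:** the target is given as "70 consecutive subjects at least 1-year post-index procedure".
- **Study Population:** eligibility is described by the operation and its date, as a "Consecutive cohort of patients who have undergone a hiatal hernia repair between 1 Jul 2015 and 1 June 2016". At least three attempts are to be made to reach each subject.
- **Study Assessments and Time Points:** chart review covers the pre-operative and peri-operative periods and then "Post-Operative (With-in 1 month of surgery"). The items in that last period include mesh- and procedure-related complications and hernia recurrence documented by imaging or endoscopy. Revision is not a named item. The only later contact is the "Minimum 1-year Follow-Up Telephone Interview", which asks "Have you had a revision surgery" together with the GERD-HRQL score and two satisfaction items. Date of surgery is collected; date of revision and date of interview are not listed.
- **Secondary Objectives:** "Identify a consecutive cohort who may be tracked long term to identify survival of repair".
- **Timeline:** "Data collection will be complete 3-months after approval and funding". No calendar start is given.
- **Deliverable(s):** a spreadsheet of the listed data and a narrative report with conclusions.
- **Statistical Analysis:** descriptive statistics and unspecified inferential statistics. No method for unequal follow-up is named.

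**The concern.** Subjects will be called at different times after surgery, all at 12 months or later and some possibly well beyond. Revision accumulates over that time. The share of subjects answering 'yes' therefore describes revision by the time of contact, over a follow-up length that varies between subjects, while the title leads a reader to expect 1-year outcomes. The data list has nothing that would convert one into the other.

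Two uses are at stake. The narrative report may present the crude percentage as a 1-year result. And the cohort is meant to be available for later tracking of how long repairs last. That work needs an event time, or at least a closed interval, for each revision and a last-known-free date for everyone else. Collecting these afterwards means re-contacting subjects or searching charts, and this center's charts may not show a revision done elsewhere.

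**Working it through.** The plan states no revision rate, so it has no figure of its own to reproduce. The check has three parts.

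**1. Spread of follow-up (from the documents).** 1 Jul 2015 to 1 Jun 2016 is 336 days, or 336/30.4375 = 11.04 months. Collection takes about 92 days, or 3.02 months. If surgeries fill the window, follow-up differs between subjects by at least 11.04 − 3.02 = 8.02 months, even if calls are made in order of surgery. If all calls fell on one day it would differ by about 11 months.

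**2. What the answers identify (no rate assumed).** Let T ≥ 12 months be the time from surgery to the call, and take recall as accurate.

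- 'No': not revised by T, so not revised by 12 months.
- 'Yes': revised somewhere in (0, T], which may be before or after 12 months.

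With k 'yes' among n interviewed, the 12-month proportion has upper limit k/n and worst-case lower limit 0. If k = 0 it is exactly 0/n. If c of the k revisions can be recognized in the first-month chart review, the lower limit rises to c/n. For n = 70 (k assumed):

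| k | lower limit (worst case) | upper limit |
|---|---|---|
| 0 | 0 | 0 |
| 2 | 0 | 2/70 = 2.9% |
| 4 | 0 | 4/70 = 5.7% |
| 6 | 0 | 6/70 = 8.6% |

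These limits hold for those interviewed. If m further eligible patients are not reached, the upper limit for the whole cohort is (k + m)/(n + m).

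**3. Possible size of the overstatement (illustration; every input is assumed).** Take p = 5% revised by 12 months, a Weibull time to revision with shape s, and surgeries spread evenly. Then λ = −ln(1 − p)/12^s, the expected crude proportion is q = E[1 − exp(−λT^s)], extra events in 70 are 70(q − p), and the chance of at least one 'yes' from after 12 months is 1 − (1 − (q − p))^70. Two call patterns:

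- **A:** calls in surgery order ending about 1 Jun 2017, T uniform from 12 to 20 months.
- **B:** calls opening about 1 Jun 2017, T = 12 + U(0, 11.04) + U(0, 3.02), from 12 to 26.1 months.

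| shape s | A: q, extra events, chance | B: q, extra events, chance |
|---|---|---|
| 0.25 | 5.35%, 0.25, 22% | 5.58%, 0.40, 33% |
| 0.5 | 5.74%, 0.52, 40% | 6.23%, 0.86, 58% |
| 1 (constant hazard) | 6.61%, 1.13, 68% | 7.80%, 1.96, 86% |
| 2 | 8.87%, 2.71, 94% | 12.36%, 5.15, 99.5% |

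For shapes 0.5 to 1, extra events run from 0.2 to 0.8 at an assumed 2% and from 1.0 to 3.7 at an assumed 10%.

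For comparison, the exact 95% CI for 4/70 is 1.6% to 14.0%, a half-width of about 6.2 points. At 5% and shapes 0.5 to 1, the excess is 0.7 to 2.8 points, well inside that. At shape 2 with pattern B it is 7.4 points, which is not.

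**The case against.** The strongest reply is that no stated analysis is broken. The primary objective concerns procedural and early post-operative safety. The secondary objectives only identify a cohort for later tracking. Nowhere is a 12-month revision proportion defined, and the plan says twice that one year is a floor. Read that way, the question asks about revision by the time of contact, and the difficulty appears only if the report gives the figure a 1-year label. This stands, and it is why the point is minor. It does not remove the point: the title does say 1-year, and timing would still be missing for later tracking even if the figure were relabeled.

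Three stronger readings are tempting, and the documents do not support them.

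- *Any 'yes' leaves the lower limit at 0.* Zero is only the worst case. A first-month revision charted as a complication would be placed before 12 months. At an assumed 5%, about a quarter of expected 'yes' answers (24% to 26%) fall in the first month under shape 0.5, and about 6% under constant hazard. Because revision is not a named chart item, this softens the bound but cannot be relied on.
- *The missing interview date matters only for describing follow-up length.* It also closes the interval for each 'yes', can nearly settle a 'yes' obtained close to 12 months, and supplies the censoring time for each 'no'.
- *The overstatement is 0.5 to 2.0 events.* That range covers only shapes 0.5 to 1 at an assumed 5%. The documents give no basis for excluding other shapes.

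It is also fair to say that charts are already a listed source and that few subjects are likely to need a second look. Re-contact or a chart search could therefore repair much of this later, at more effort and less reliably.

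**Conclusion.** The point holds, with minor weight. Following the plan as written, the timing of any revision after the first month is unknown, and no 12-month figure can be computed unless nobody answers 'yes'. The firm result is the bound: k/n above, and 0 in the worst case below, among those interviewed and given accurate recall. The direction is also firm: read as a 12-month percentage, the crude figure may be correct or too high, but not too low.

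The size of the excess is not firm. At an assumed 5% revised by 12 months it is about 0.5 to 2.0 extra events in 70 for Weibull shapes 0.5 to 1, and about 0.25 to 5.2 for shapes 0.25 to 2, under assumed call dates. A reader might infer that a planned 1-year endpoint is invalid or that the safety conclusions are compromised. Neither follows, because no such endpoint is defined and the primary objective rests on procedural and first-month data.

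**What to change.** Before the calls start:

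1. Add to the data list, for subjects who answer 'yes': *If yes, in what month and year was the revision?* (the first, if more than one). Check it against the chart where available.
2. Add the interview date for every subject.
3. Align the data use agreement and consent script. Subjects are currently told that, apart from information needed for age and date of surgery, no protected health information is used.

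In the report:

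- Give the proportion of interviewed subjects revised within 12 months of surgery, with an exact 95% CI and the number interviewed out of the cohort.
- List later revisions separately with time since surgery.
- Where a 'yes' stays undated, or falls in the anniversary month and cannot be resolved, give the lower and upper bound.
- State the median and range of time since surgery for all interview outcomes.
- If no revision dates are obtained, call the figure *revised by interview*, with that median and range, and not 1-year.

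The cost is one extra question for the subjects who answer 'yes', one date field per call, and a small consent, data-use-agreement and IRB check. The downside is some recall error in revision dates, which a chart check removes only in part.

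### Telephone consent at one year or later decides whose charts count towards the early-safety objective, so the safety rate would describe consenting survivors, not the consecutive operated cohort

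*Combined protocol and SAP*

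**What the plan says.** All of these rows are in the combined protocol and SAP.

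- **Study Objectives, primary:** "Characterize the procedural and early post-operative safety profile of MIROMESH when used as reinforcement in hiatal hernia repair". Under Study Assessments and Time Points, the data for this are chart items: peri-operative complications, and complications, dysphagia, stenosis and dilations within one month of surgery.
- **Informed Consent:** "All subjects will be required to give verbal consent, via the telephone interview, for participation in this study". The only interview described is the one at a minimum of one year. The row continues: "They will be informed that historical data regarding their pathology and procedure will be gathered".
- **Study Population:** "Consecutive cohort of patients who have undergone a hiatal hernia repair between 1 Jul 2015 and 1 June 2016", and "A minimum of three attempts to reach each subject in the cohort shall be made".
- **Planned Sample Size:** "70 consecutive subjects at least 1-year post-index procedure".
- **Study Design:** "This will be a retrospective chart review to identify the appropriate cohort with a prospective follow-up survey to acquire safety and outcome information".
- **Project Budget:** "25% Upon receipt of spreadsheet showing 50% (35 subjects) completion", followed by a payment when the data for all 70 subjects have been received.

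The Statistical Analysis row calls for descriptive statistics, and for inferential statistics on change over time. It names no analysis set, no safety denominator and no handling of patients who do not take part.

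**The concern.** The early-safety outcome is complete one month after surgery. Under the consent row, whether a patient belongs to the study is settled at least eleven months after that, by whether the patient can be reached and agrees. Entry to the denominator is thus decided after the outcome has occurred.

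The clearest consequence is for deaths. A patient who died of an early complication cannot give consent by telephone, so the event could not be counted in the primary result, even though the chart fields for complications would hold it. Patients who moved away or declined would drop out in the same way. The cohort in the sample-size and population rows is called consecutive, and a rate in those who consented would not be a rate in that cohort. Because the plan does not say what the 70 counts, a reader of the report could not tell which rate was being given.

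**Working it through.** **Step 1. Which patients' charts enter?** Set the rows side by side.

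- *Consenters only.* The consent row applies to all subjects, ties participation to the telephone interview, and speaks of the historical data as still to be gathered. The payment rows fit this: they count subjects by completion and by full data, and the data listed include the interview items.
- *All operated patients.* The population row defines the cohort by having been operated on in a closed window. The design row uses the charts to identify it. The contact rule applies to every subject in the cohort, so subject there includes people not yet reached.

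The first reading is the more natural one. Identifying a cohort from charts may be no more than screening, and three contact attempts fit entry by consent equally well. The second has some support because the word subject is used loosely. No other row settles the matter; the chart review is of appropriate subjects, a term left undefined.

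**Step 2. The plan's own figures.** The half-way payment is consistent: 50% × 70 = 35. The 70 itself cannot be reproduced, because no event rate, precision target or expected participation is stated.

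**Step 3. Bounds if the 70 are operated patients.** Let k be the number left out and x the events among the 70 − k who consent. The full-cohort rate lies between x/70 (none of those left out had an event) and (x + k)/70 (all did). The width is k/70 whatever x is. The values of k are assumed.

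- k = 7: 7/70 = 10 percentage points.
- k = 14: 14/70 = 20 percentage points. For example, with an assumed 6 events among 56 consenting patients (10.7%), the bounds are 6/70 = 8.6% and 20/70 = 28.6%.

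**Step 4. Bounds if the 70 are consenting patients.** With assumed participation r, the number operated is N = 70/r rounded up, N − 70 are left out, and the width is (N − 70)/N.

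| Assumed r | Operated N | Left out | Width (percentage points) |
|---|---|---|---|
| 90% | 70/0.9 = 77.8, so 78 | 8 | 8/78 = 10.3 |
| 80% | 70/0.8 = 87.5, so 88 | 18 | 18/88 = 20.5 |
| 70% | 70/0.7 = 100 | 30 | 30/100 = 30.0 |

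These widths are extremes, not estimates of bias.

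**The case against.** The strongest reply is that the document is a summary. The consent script is not in the supplied text, nor is the IRB's decision, and either may deal with charts of patients who are not interviewed. This stands as a limit on confidence. It does not remove the point, because the Ethical Considerations row says that this summary is what the IRB will review.

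It can also be said that the study is descriptive, with no comparator and no safety hypothesis, so that clear labelling would be enough. That is partly right, and labelling is the fallback below. But a descriptive rate still needs a stated denominator.

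Four stronger inferences are tempting, and the documents do not support them.

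- *The plan is evenly split between two readings.* It is not; the consent text favours consenters only.
- *The consecutive label also fails in the secondary objectives.* Those require only that a cohort be identified for later tracking. A cohort can be identified consecutively and then followed incompletely.
- *The readings will almost surely give materially different rates.* At an assumed 98% independent participation, the chance that all 70 take part is 0.98^70 = 24.3%. That shows only that the two groups probably differ by at least one patient. Expected omissions are 70 × 0.02 = 1.4, or at most about 2 points on average.
- *The safety rate will be too low.* Deaths push that way, but patients with problems may be harder or easier to reach, so the net direction is unknown.

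**Conclusion.** The point holds as a selection problem in the primary safety denominator. Followed as written, the consent row limits early safety to patients alive, reachable and willing at one year or later. A fatal early complication would go uncounted, and the consecutive label in the sample-size and population rows would not describe the patients analysed. What the 70 counts is also undefined.

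No bias can be estimated, since neither a participation rate nor a complication rate is given. Under assumed omissions of 7 or 14 from 70 operated patients, the full-cohort rate is uncertain by at most 10 or 20 points. Confidence is moderate because the consent script was not available. This is a cheap improvement.

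**What to change.** 1. Revise the Informed Consent row and the telephone script, including the mailed copy, so that verbal consent governs the interview.
2. Ask the IRB to permit chart review of all eligible MIROMESH repairs in the window under the planned limited data set agreement, at least for deceased and unreachable patients, with an IRB-approved rule for the charts of those who decline.
3. Analyse early safety on all permitted charts, and interview outcomes on those interviewed.
4. State whether the 70 are operated or consenting patients, in the sample-size row and the payment milestones.
5. Report the numbers operated, known to have died, unreachable after at least three attempts, declined and interviewed.

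If the IRB does not permit this, label the safety rates as applying to consenting survivors and give the best-case and worst-case bounds of Step 3 or 4 for the full operated cohort.

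**Cost.** One IRB request, whose outcome the documents cannot predict; a revision of text and script; and possibly a small change to the payment milestones, since the budget is fixed at $15,000 plus IRB fees. No extra charts are needed if the 70 are operated patients. If they are consenting patients, up to 8, 18 or 30 more charts are needed at an assumed 90%, 80% or 70% participation (at the last, 30/70 = 43% more abstraction), within the three-month data collection period. The fallback is a reporting change only.

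### Does the plan need to say how the complication items behind the primary safety objective will be summarised?

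*Combined protocol and SAP*

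**What the plan says.** The Statistical Analysis section of the combined protocol and SAP has two sentences. The first provides for descriptive statistics, "including but not limited to mean, standard deviation, frequency and percentages will be used to describe demographics, medical history, and characterize baseline variable". The second reads "Inferential statistics will be used to describe changes in variable over time".

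The data list is under Study Assessments and Time Points. The peri-operative block ends with "Length of stay • Complications", a single undivided complications entry. The block for the first month has "Complications (Mesh related)", a matching procedure-related entry, and then "Prolonged dysphagia (Y/N) • Stenosis (Y/N) • Dilations (Y/N) • EGD/UGL documented hernia recurrence • GERD-HRQL Score". GERD-HRQL also appears before surgery ("test (% acid exposure in 24 hours) • GERD-HRQL Score") and at the telephone interview ("Have you had a revision surgery? • GERD-HRQL Score").

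The Deliverable(s) section promises a spreadsheet of all the listed data and a "Narrative study report outlining results and drawing conclusions". The planned sample size is 70 consecutive subjects, with no power or precision calculation behind it.

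**The concern.** Complications come first in the study title and early safety is the primary objective. Read literally, the two statistical sentences cover baseline description and change over time. The complication items fit neither: they are not baseline variables, and none is listed before surgery, so they have no change to estimate. The open-ended phrase in the first sentence widens the list of statistics, not the list of variables.

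Two consequences seem to follow. First, a report could state that no events occurred, or very few, without showing how little 70 patients can exclude. Second, one patient may have stenosis, a dilation and a procedure-related complication, so a table of item percentages need not show how many patients had any problem. The operations date from July 2015 to June 2016, so the early outcomes were already in the charts and the summary could be chosen with the results in view.

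**Working it through.** **Is the omission real?** Set the two statistical sentences against the data list:

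- Demographics, medical history and baseline: covered by the first sentence.
- GERD-HRQL, listed at three time points: fits the second sentence.
- Peri-operative complications and, within a month, mesh-related complications, procedure-related complications, dysphagia, stenosis, dilations and documented recurrence: named in neither.

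The omission is real. The plan has no figure of its own to reproduce here, because N = 70 comes without a stated rate, precision or confidence level.

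**How much uncertainty could go unstated?** Inputs: N = 70 (Planned Sample Size); a two-sided 95% level (assumed); event counts (assumed). The exact Clopper-Pearson limits for x events in n are the 2.5% quantile of Beta(x, n − x + 1) and the 97.5% quantile of Beta(x + 1, n − x). For x = 0 the upper limit reduces to 1 − 0.025^(1/n).

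| Events / N | Proportion | Exact 95% CI |
|---|---|---|
| 0/70 | 0% | 0 to 5.1% |
| 1/70 | 1.4% | 0.04 to 7.7% |
| 3/70 | 4.3% | 0.9 to 12.0% |
| 5/70 | 7.1% | 2.4 to 15.9% |

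The Informed Consent section requires verbal consent by telephone, so fewer than 70 may be analysed. For zero events the upper limit is 1 − 0.025^(1/60) = 6.0% at an assumed 60 patients and 1 − 0.025^(1/50) = 7.1% at 50. A complication with a true rate of 1% would be missed altogether in 70 patients with probability 0.99^70 = 0.495.

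Every one of these limits follows from n and N. A report that gives counts and denominators, the ordinary use of the frequencies and percentages already named, hides nothing that a reader cannot work out.

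**How much could overlap hide?** Suppose, purely for illustration, that dysphagia, stenosis and dilation are each recorded in 3 of 70 patients. The number with at least one lies between max(3, 3, 3) = 3 (4.3%, CI 0.9 to 12.0%) and 3 + 3 + 3 = 9 (12.9%, CI 6.1 to 23.0%). The bounds are arithmetically right but are combinatorial extremes. Nine requires that no patient who was dilated had either stenosis or prolonged dysphagia recorded. No count in the documents supports either end.

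**Can the patient count be obtained?** Dysphagia, stenosis and dilations carry a yes/no format, which is naturally one answer per patient, so for them the unit is already the patient. Only the complications entries leave patients versus events open. The Project Budget milestones tie payment to a spreadsheet with data on all 70 subjects. On the natural reading of one record per subject (an assumption), the number with any given combination is a direct count.

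**The case for a change.** The best case for a change is that the remedy is a few sentences, concerns the primary objective itself, and would remove any suspicion that the summary was picked after the results were seen. A reader of the narrative report, unlike a holder of the spreadsheet, cannot rebuild the number of affected patients from item percentages.

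Part of this stands. The section is thin, and naming the complication items would have been better drafting. But the argument about the reader assumes that the report will leave the patient count out, and nothing in the documents suggests that.

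The obvious remedy, a pooled proportion with at least one of seven items, brings difficulties of its own. No section assigns those seven items to the primary objective, and documented recurrence fits the secondary objective on survival of the repair at least as well. Dilation is a treatment rather than a complication. Recurrence depends on endoscopy or upper-GI imaging that the plan does not schedule for everyone, so the pooled figure would lack a clear denominator. Nor does it matter to such a count whether a yes for stenosis is also entered as a complication, since each patient is counted once.

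**Conclusion.** No change is needed. The Statistical Analysis section does leave the complication items unnamed, but this is missing detail and not a rule that gives a wrong answer. The tools it names suit the items, and the promised spreadsheet supports patient-level counts. The study is descriptive, with no hypothesis or decision threshold that a choice of summary could tip. An analyst would report patients affected over patients with data for each item, and would give recurrence its own denominator of those examined.

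The quantity at stake is modest and recoverable: an upper limit of 5.1% after zero events in 70, or 7.1% if only 50 were analysed. The threefold spread from overlap rests on invented counts at their extremes and carries no weight. The conclusion assumes a two-sided 95% level, one record per subject, and a report that gives counts with denominators.
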